### **6.1. Eligibility Assessment**

All subjects who completed the full study period in the main ADORE study, will sign the extension study-specific consent form. The procedures for Visit 6 or 8 of the main ADORE study will be considered for the baseline visit for the extension study. In case the ADOREXT study is not fully set up at the time of subject's finalization in the main ADORE study, baseline visit could take place up to 6 weeks after finalization. Study assessments performed at Visit 6 or 8 of the main study can be used as baseline assessments of the open label extension ADOREXT study within the allowed 6 weeks period.

A signed copy of the informed consent form (ICF) should be provided to each consenting subject and with the original to be retained in the subject's study records.

#### Baseline Assessments

### **6.2. Baseline (Visit 1)**

The following procedures, performed at Visit 6 or 8 of the main study, will be considered as baseline procedures for the extension study:

- Review inclusion and exclusion criteria.
- Review ongoing concomitant medications.
- Complete physical examination.
- Neurological examination.
- Weight.
- Vital signs measured with the subject in a supine/semi-supine position (for at least 5 minutes prior), including blood pressure, pulse rate, respiratory rate, pulse oximetry and temperature.
- Standard 12-lead ECG (subject should be in a supine/semi-supine position for at least 5 minutes prior to assessment).
- Blood samples for routine clinical labs (clinical chemistry, haematology). See table 2 for lab assessments.
- Blood sampling for biomarkers: neurofilament light (NFL). Creatinine and creatine kinase will be measured in routine biochemistry lab testing.
- Urine collection for biomarkers: urinary extracellular domain of neurotrophin receptor p75 (Urinary P75ECD) and oxidative stress biomarker 8-hydroxyguanosine (8-OHdG).
- Blood sampling for genotyping for Future Biomedical Research (FBR) (if consented).

- Urine samples for urinalysis or dipstick testing
- Urine pregnancy test only in women of childbearing potential.
- Plasma pyridoxal 5'-phosphate (PLP) levels, and, if necessary, vitamin B6 supplements (pyridoxine (100 mg/day)) will be prescribed.
- ALS evaluation procedures: ALSFRS-R, Slow Vital Capacity (SVC), ALSAQ-40, EQ-ED-5L, VAS, King's staging system and, MiToS
- Cost questionnaire.
- Adverse Events monitoring.
- ECAS.
- Study drug administration
- Dispense study medication

### 6.3. Rest of visits

Every 3 months and up to the product is marketed, subjects will attend the study site and the following procedures will be performed:

- Review ongoing concomitant medications.
- Complete physical examination (every 6 months).
- Neurological examination (every 6 months).
- Weight.
- Vital signs measured with the subject in a supine/semi-supine position (for at least 5 minutes prior), including blood pressure, pulse rate, respiratory rate, pulse oximetry and temperature.
- Standard 12-lead ECG (subject should be in a supine/semi-supine position for at least 5 minutes prior to assessment) (every 6 months).
- Blood samples for routine clinical labs (clinical chemistry, haematology). See table 2 for lab assessments.
- Urine samples for urinalysis or dipstick testing.
- Blood sampling for biomarkers: neurofilament light (NFL) (every 12 months).
- Urine collection for biomarkers: urinary extracellular domain of neurotrophin receptor p75 (Urinary P75ECD) and oxidative stress biomarker 8-hydroxyguanosine (8-OHdG) (every 12 months).
- Urine pregnancy test only in women of childbearing potential.
- Plasma pyridoxal 5'-phosphate (PLP) levels, and, if necessary, vitamin B6 supplements (pyridoxine (100 mg/day)) will be prescribed.
- ALS evaluation procedures: ALSFRS-R, Slow Vital Capacity (SVC), ALSAQ-40, EQ-5D-5L, VAS, King's staging system and, MiToS.
- Adverse Events monitoring.
- ECAS (every 6 months).
- Vital status (tracheostomy or initiation of non-invasive ventilation for more than 20 hours a day for more than 10 consecutive days) / Date of death. Cost questionnaire
- Dispense study medication

#### 6.4. Phone contacts

Patients not willing to receive or continue receiving active treatment in the extension study or that had already discontinued study treatment during the course of the main ADORE study for safety reasons, will be asked to be contacted by phone every three months and followed up for vital status. These patients will not undergo the baseline assessments or any other study procedures.

**Table 2: Overview of laboratory assessments**

Haematology	Chemistry	Urinalysis/Dipstick
Haematocrit	Bilirubin (direct) and Bilirubin (total)	Blood
Haemoglobin	Alkaline phosphatase	Glucose
RBC	Alanine aminotransferase (ALT)	Protein
Platelet count	Aspartate aminotransferase (AST)	Specific gravity
WBC	Bicarbonate	Microscopic exam, if abnormal results are noted
Differential count:	Calcium	Ketone
Basophils	Chloride	PH
Eosinophils	Creatinine	Nitrite
Lymphocytes	gammaGT (GGT)	Leukocytes
Monocytes	Glucose	Bilirubin
Neutrophils	Potassium	Urobilinogen
Large Unstained cells	Sodium	
	Uric Acid	
	Total protein	
	Urea (BUN)	
	eGFR	
	Activated partial thromboplastin time (aPTT)	
	Prothrombin Time (PTT)	
	Fibrinogen	
	Lactate dehydrogenase (LDH)	
	Creatinine kinase (CK)	
	Vitamin B6	

Blood and urine samples for routine clinical chemistry, haematology and urinalysis/dipstick will be analysed locally.

Vitamin B6 will be analysed by a central laboratory.

Instructions for handling, shipment and storing of blood and urine samples for Biomarkers testing will be described in a separate laboratory manual.

## 6.5. Early Discontinuation/Withdrawal of Participants

Subjects may withdraw consent at any time for any reason or be discontinued from the extension trial at the discretion of the investigator should any untoward effect occur. In addition, a subject may be withdrawn by the investigator or the Sponsor if enrolment into the trial is inappropriate, the trial plan is violated, or for administrative and/or safety reasons.

In this trial, a subject may discontinue from treatment but continue to participate in the regularly scheduled activities, as long as the subject does not withdraw consent.

A subject must be discontinued from the trial for any of the following reasons:

- The subject withdraws consent.
- The subject has a medical condition or personal circumstances which, in the opinion of the investigator and/or Sponsor, places the subject at unnecessary risk if participation in the trial is continued.

A subject must be discontinued from study treatment (but should continue to be monitored in the study) for any of the following reasons:

- 1) Key safety assessment cannot be performed.
- 2) The subject becomes pregnant during the study.
- 3) The subject's investigator considers it is in the best interest of the subject to discontinue.
- 4) Serious adverse event considered related to the IMP
- 5) Severe Neurotoxicity considered related to the IMP
- 6) Any other severe adverse event considered related to the IMP at the discretion of the investigator.
- 7) Acute renal failure (creatinine clearance of less than 30 mL/min)
- 8) Severe liver disorder defined as:
  - a. ALT/AST  $\geq$  3xULN and bilirubin  $\geq$  2xULN (>35% direct bilirubin).
  - b. ALT/AST  $\geq$  8xULN.
  - c. ALT/AST  $\geq$  3xULN and with symptoms believed to be related to liver injury or hypersensitivity.
  - d. ALT/AST  $\geq$  3x baseline ALT/AST and with symptoms believed to be related to liver injury or hypersensitivity.
  - e. ALT/AST  $\geq$  5xULN and ALT/AST  $<$  8xULN that persists more than two weeks.
- 9) Acute lung injury with pyrexia, cough, dyspnoea and chest X-ray abnormality.
- 10) Rhabdomyolysis.
- 11) Disseminated intravascular coagulation (DIC).
- 12) Hypersensitivity reaction
- 13) Anaphylactic reaction/shock
- 14) Thrombocytopenia
  - a. Platelets  $<$  20  $10^9/L$  or  $>$  1000  $10^9/L$
  - b. Platelets between 20 and 50  $10^9/L$  if in the investigator judgement the patient present risk of any kind of bleeding or haemorrhage.
- 15) Neutropenia of  $\leq$  0.5  $10^9/L$

The Sponsor reserves the right to terminate the extension study at any time if continuation of the protocol would present a potential safety risk to the subjects or in case that after the analysis of the main ADORE study it is concluded that there is no clinical benefit for the patients.

Patients who withdraw due to an Adverse Event (AE) or Serious Adverse Event (SAE) will be given appropriate care under medical supervision until the symptoms resolve or the patient's condition becomes stable.

## 7. STUDY INTERVENTIONS

### 7.1. Investigational Medicinal Product(s) (IMP) Description

Compound name: FAB122

INN/generic name: edaravone

Synonyms: norphenazone; methylphenylpyrazolone; norantipyrine

[figure not shown]
IUPAC name: 3-methyl-1-phenyl-4, 5-dihydro-1H-pyrazol-5-one

CAS name: 5-Methyl-2-phenyl-1, 2-dihdropyrazol-3-one (CAS Registry No. 89-25-8)

Molecular formula: C10H10N2O

Chirality: FAB122 has no chiral centre

Structural formula:

Molecular weight: 174.20 g/mol

Appearance: off-white to white powder

Solubility: sparingly soluble in water, soluble in acetic acid and methanol,  
limited solubility in ethanol

Hygroscopicity: FAB122 is not hygroscopic

Each sachet of the active treatment contains the following composition given in the table 3:

**Table 3: The theoretical quantitative composition of FAB122 granules for oral solution in sachet**

Component	Amount/sachet
FAB122	100.0 mg
Spray dried mannitol 200	621.8 mg
Disodium hydrogen phosphate dihydrate	363.6 mg
Sodium Laurilsulfate (SLS)	5.5 mg
Total	1090.9 mg

---

The active ingredient and the investigational drug have been produced complying the Good Manufacturing Practices of the European Union for active pharmaceutical ingredients and ICH Q7A guidelines.

Study treatment is supplied as granules for oral solution, 100 mg FAB122 per sachet, to be dissolved in about 100 ml water approximately and stirred slightly by a teaspoonful. Study treatment must be administered immediately after its dissolution.

First dosing will be administered at the study site and patients will be instructed about study treatment administration.

Study treatment should be administered once a day at about the same time each day. Dosing needs to be done each morning under fasting conditions. This implies taking the dose: at least two (2) hours after a meal or snack and 30 min after a drink AND no eating or drinking for at least one-hour post dosing. If a subject misses a dose, the missed dose should be taken as soon as possible taking the fasted conditions into account if feasible. If the time period until the regular dosing time for the next dose is less than 4 hours, then the missed dose should be skipped, and the normal dosing schedule should be resumed. The next dose should not be doubled in order to make up for the missed dose.

The study medication is to be stored in the refrigerator at a temperature between 2 - 8 °C. Temperature excursions are permitted at 8-25°C not exceeding 72 hours. Please contact the Sponsor in case the temperature excursion is on different conditions from the ones mentioned before.

Study treatment could be given via gastrostomy and feeding tube if applicable.

#### **7.1.1. Packaging and Labelling**

The label(s) for the investigational product will include all information according to GMP Annex 13. Additional information may be included on the label as applicable per local regulations.

#### **7.1.2. Compliance with Trial Treatment**

Patients will be instructed to return all used an unused medication at each study visit. The number of sachets dispensed and returned will be registered by the investigator at each visit to obtain information on patients' compliance. The patient will be considered compliant with treatment when > 80%-100% of the total scheduled doses since the last clinic visit are administered.

Investigational product used in this study will be monitored for compliant usage throughout the trial by the Sponsor or their designee.

#### **7.1.3. Accountability of the Trial Treatment**

Adequate supplies of the IMP will be provided to the site. Study drug should be stored in the original package under conditions as stated on the product label, in a secure, temperature-monitored, locked area, under the responsibility of the Investigator or other authorized individual until dispensed to the subjects.

The pharmacy of the site must maintain accurate records of the receipt of all study drug, including date received, lot number, expiration date if applicable, amount received, condition of the package, and the disposition of all study drug.

Current dispensing records will also be maintained, including the date and amount of medication dispensed and the identity of the subject receiving the medication.

At the end of the study, it must be possible to reconcile delivery records with those of used, partially used and returned stocks.

All used and unused IMP must be returned to the storage/distribution facility after the study is completed.

In accordance with local regulations, in case it is necessary, and the site has not a specific procedure in place to deliver drugs directly to patients, IMP can be delivered directly to patient's home, through a validated direct to patient service provided by the Sponsor.

#### **7.1.4. Concomitant Medication**

Treatment of ALS impairments (nutrition, respiration, motricity, communication) will be done with a multidisciplinary approach and accordingly to European Federation of Neurological Societies (EFNS) Guidelines for ALS patients' management.

#### **7.2. Other Treatments (non-IMPS)**

Riluzole (100 mg/day or less) may be used as background (add-on) therapy.

---

## 8. PARAMETERS AND METHODS OF ASSESSMENT

### 8.1. Parameters

#### 8.1.1. ALSFRS-R

The ALSFRS-R is a validated 12-item questionnaire designed to evaluate the functioning of respiratory, bulbar, fine and gross motor function in ALS patients. The total score ranges from 48 (no limitation in daily activities) to 0 (total inability). The patients will be asked to complete the ALSFRS-R questionnaire at each in-clinic visit. The total score of the ALSFRS-R and the score of each subdomain will be recorded in the eCRF by the investigator or designee.

#### 8.1.2. Survival Time

If a patient dies over the study period, the date of death will be recorded in the eCRF. If a patient reaches the criteria for respiratory insufficiency (tracheostomy or the use of non-invasive ventilation for >20 hours per day for >10 consecutive days), the date this criterion was met will be recorded in the eCRF and the patient will no longer be part of the study.

#### 8.1.3. Lung Function

Lung function is evaluated by using a non-invasive spirometer to determine the Slow Vital Capacity (SVC). During the test, the patient inspires fully and then slowly expires all the air in his/her lungs. The test will be done using a facemask. This procedure is repeated 3 times minimally until a steady recording is obtained; the highest score is recorded. A digital spirometer is used to determine SVC values. The SVC will be assessed at each in-clinic visit. The results of SVC in liters will be recorded in the eCRF by the investigator or designee.

#### 8.1.4. Staging of Disease Progression

The King's staging system is a simple clinical staging system, which defines four stages of ALS. The first three stages are defined by functional involvement of a region: bulbar, upper limbs and lower limbs. The number of regions involved gives the stage. Stage 4 is reached if swallowing (4A) or respiratory (4B) difficulty is severe enough to require intervention. MiToS is a similar clinical staging system, in which the stages are defined as loss of independence on the four domains of the ALSFRS-R: swallowing, walking/self-care, communicating and breathing. The investigator will assess both staging systems for each patient and will record the results in the eCRF.

#### 8.1.5. Health Status

ALSAQ40: The Amyotrophic Lateral Sclerosis Assessment Questionnaire is a patient reported outcome (PRO) designed to determine the patient's health status. The ALSAQ40 is specifically used to measure the subjective well-being of patients with ALS. There are 40 items/questions in the long form, the ALSAQ40, with 5 discrete scales: physical mobility (10 items), activities of daily living and independence (10 items), eating and drinking (3 items), communication (7 items), emotional reactions (10 items). During the study the

---

questionnaire will be provided in the local language of the patient. The ALSAQ40 questionnaire will be completed by the patient at each study visit via a study App or online questionnaire. In case of technical issues with the ePRO device these questionnaires can be completed on a paper version as a backup.

EQ-5D-5L is a patient reported outcome (PRO), simple, valid, standardized health state measure. It consists of five questions that relates to five dimensions of health: mobility, self-care, usual activities, pain/discomfort and anxiety/depression. Each dimension/question can be scored on five levels of severity (1, no; 2, slight; 3, moderate; 4, severe; 5, extreme problems). In addition, responders will be asked to rate their current health related quality of life (HRQoL) on a visual analogue scale (VAS) ranging from 0 (bad) to 100 (very good). During the study the questionnaire will be provided in the local language of the patient. The EQ-5D-5L and VAS will be completed at each study visit via a study App or online questionnaire. In case of technical issues with the ePRO device these questionnaires can be completed on a paper version as a backup.

#### **8.1.6. Cognition**

The neuropsychological status of patients will be evaluated using the Edinburgh Cognitive and Behavioral ALS Screen (ECAS). The ECAS is independent of motor disability and evaluates five cognitive domains: language functions, executive functions, letter fluency, memory and visuospatial functioning. The ECAS is designed for ALS patients and answers can be given verbally, or by a combination of writing or pointing. It is suitable for patients who are anarthric or patients who have no hand motor function. The total score is 136 points and should take no longer than 15 minutes to administer. The ECAS will be completed by the investigator or designee at each study visit.

#### **8.2. Safety Parameters**

Occurrence of AEs, changes on physical examination (including body weight), vital signs, ECG parameters and laboratory examinations (biochemistry, haematology and urinalysis) will be registered throughout the entire study duration.

All AEs will be actively collected at each visit, from spontaneous declarations of the patient as well as from oral inquiry and clinical examination. All concomitant medications and/or therapies should be documented in the patient file and reported in the electronic Case Report Form (eCRF).

##### **8.2.1. Physical and neurological examination**

Physical examinations will be performed by qualified personnel according to the Schedule of Events. Symptom directed physical exams will be performed as applicable. Physical examination includes the following assessments: general appearance, head, eyes, ears/nose/throat, neck, lymph nodes, skin, lungs, heart, abdomen, musculoskeletal, and neurologic evaluations. Breast, rectal, and genitourinary/pelvic exams should be performed when clinically indicated. Weight (kilograms) will be measured as part of all physical examinations. Height (centimeters) will be measured only at the baseline visit. The BMI will be calculated.

---

Neurological examination will be performed by qualified personnel according to the Schedule of Events to assess possible peripheral nerve dysfunction (= sensory or motor symptoms), diminished or absent reflexes (compared with baseline examination), sensory abnormalities (e.g. numbness or tingling) or weakness. In case a subject experiences clinical signs or symptoms at home, subjects will be asked to contact the clinic. All abnormal findings will be documented in the database.

#### **8.2.2.     Laboratory Parameters**

The results of all clinical laboratory tests conducted during the study must be assessed by the investigator to assess patients' safety.

Any significant abnormalities is to be documented and followed up as AEs and should be fully investigated. Whenever possible, the etiology of the abnormal findings will be documented in the database. Laboratory results with significantly abnormal values should be investigated as such and checked for verification. Additional tests and other evaluations required to establish the significance or etiology of an abnormal result or to monitor the course of an AE should be obtained when clinically indicated. In particular, if a clinically significant abnormal result is observed that is not resolved by the final study visit, repeat tests will be performed if possible and resolution or stability of the abnormality will be recorded in the source documentation.

Any significant laboratory abnormalities that are either serious or unexpected will be promptly reported to the Sponsor's Medical Monitor. Any additional relevant laboratory results obtained by the investigator during the course of this study will be reported to the Sponsor or its representative.

#### **8.2.3.     ECG**

Twelve-lead ECGs will be performed according to the Schedule of Events. Subject should be resting supine/semi-supine for at least 5 minutes prior to all ECG measurements if possible.

#### **8.2.4.     Vital Signs**

Vital signs, including blood pressure, heart rate, respiratory rate, pulse oximetry, and temperature, will be measured at study visits according to the Schedule of Events. Subject should be resting supine/semi-supine for at least 5 minutes prior to vital signs measurements.

---

## 9. SAFETY REPORTING

Adverse events will be recorded (using MEDRA version 23.0) beginning immediately after the ICF is signed. The investigator (and/or designee) must document all AEs reported by the subject from the signing of the ICF through completion of the final follow-up. Any subject who is withdrawn from the study due to an AE shall be followed until the outcome of the event is determined, and the investigator will document available follow-up information on the subject's database.

### 9.1. Definitions

#### 9.1.1. Adverse Event

An AE is any unfavorable and unintended sign (including an abnormal laboratory finding), symptom, or disease temporally associated with the use of a medicinal (investigational) product, whether or not related to the medicinal (investigational) product. An AE is any symptom, sign, illness, or experience that develops or worsens in severity during the course of the study. Adverse events reported after consent but before the first dose of study drug are still to be documented by the investigator but will be considered non-treatment-emergent AEs.

Intercurrent illnesses or injuries should be regarded as AEs. Abnormal results of laboratory tests or diagnostic procedures are considered to be AEs if the abnormality:

- Is associated with clinical signs or symptoms.
- Is considered by the investigator to be of clinical significance.
- Results in study withdrawal.
- Fulfills any of the criteria for a SAE, as described in this section.
- Requires intervention or further evaluation to determine the etiology of the abnormality and/or assess the risk to the subject.
- Requires treatment.

Changes in ALS symptoms will not be documented as AEs unless they are extraordinary and/or unexpected.

A treatment-emergent adverse event (TEAE) is defined as an adverse event observed after the first dose of study drug. If a subject experiences an event both prior to and after starting study drug administration, the event will be considered a TEAE (of the treatment) only if it has worsened in severity (i.e., it is reported with a new start date) after study drug administration of the specific treatment, and prior to the start of another treatment, if any.

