## 2. INTRODUCTION

### 2.1. Background and rationale

#### Disease under investigation

ALS is a devastating and fatal condition (Bruijn et al., 2004; Shook and Pioro, 2009) characterized by progressive degeneration of upper and lower motor neurons (Elbasiouny et al., 2012). Degeneration of lower motor neurons (LMN) results in loss of muscle strength, muscular atrophy, hyporeflexia, hypotonicity, fasciculations, flaccidity and or muscle cramps. If the upper motor neurons (UMN) degenerate, symptoms of spasticity and pathologic hyperreflexia may occur. ALS eventually results in death, usually due to respiratory failure (Brown and Al-Chalabi, 2017; Hardiman et al., 2017; Maurer, 2012; van Es et al., 2017).

Average disease duration is 2-5 years from the first symptoms until death, but it may vary between a few months to over twenty years (Westeneng et al., 2018). About one-third of the patients present with speech and swallowing difficulties, whereas others report progressive weakness in the hands, arms or legs. Respiratory symptoms are the initial signs in 2-3% of the patients and are associated with a poorer prognosis (Gautier et al., 2010; Shoesmith et al., 2007). Respiratory failure is the cause of death in 66-81% of the patients with ALS (Gil et al., 2008; Spataro et al., 2010; Yang et al., 2011).

The crude worldwide ALS prevalence is 4.42 (95% CI 3.92–4.96) per 100,000 population and the worldwide incidence is 1.59 (95% CI 1.39–1.81) per 100,000 person-years. In West Europe the prevalence is 9.62 (95% CI 4.80–16.10); and the incidence is 2.76, (95% CI 2.00–3.64) per 100,000 person-years. (Global variation in prevalence and incidence of amyotrophic lateral sclerosis: a systematic review and meta-analysis - PubMed (nih.gov)).

It occurs mostly in the range of 40-60 years, although ALS can occur at any adult age. Approximately 10% is classified as familial ALS (fALS) and 90% as sporadic ALS (sALS). For the familial form, more than 40 genes have been identified to date, which together account for about 15% of cases (Recent advances in the diagnosis and prognosis of amyotrophic lateral sclerosis - PubMed (nih.gov)).

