## **2.2. Risk-Benefit Assessment**

ALS is a devastating neurological disease for which there is no cure and an urgent unmet need persists for effective therapies. The main aims in the care of these patients are to minimize morbidity and maximize quality of life. Riluzole and iv edaravone are the only current approved drugs for ALS.

In general, long-term treatment with intravenously administered edaravone showed clinical benefit and an acceptable safety profile in ALS patients. As well, single- and multiple dose of FAB122 was safe and well tolerated in ALS patients and healthy volunteers (FAB122 IB).

Overall, the safety and efficacy of edaravone administered by oral and intravenous routes have been demonstrated in many clinical trials in healthy volunteers and ALS patients. Also, a phase III clinical trial (ADORE) with daily oral edaravone is being conducted by Ferrer in 300 patients with ALS.

At the time of writing of this version of the protocol, all patients have been recruited in the main study ADORE and there are patients participating for up to 72 weeks. No safety concerns have been raised during the monthly safety data review by the Data Safety Monitoring Board (DSMB). The DSMB specially reviewed the data related to potential neurotoxicity and concluded that there is low incidence of neuropathies and abnormalities detected in NCS assessments.

Therefore, the expected clinical benefits from the participation in the current OLE study for selected patients overcome the potential risks.

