### **5.6.2 Other safety endpoints and examinations**

Not applicable / not in the scope of this SAP following early termination of the study.

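### No planned output shows the neurological-examination findings, although motor or reflex worsening judged to be ALS can go unrecorded as an adverse event

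*Protocol*

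**What the plan says.** Neurotoxicity is a risk the protocol itself singles out. Protocol 2.2 reports of the main study that "The DSMB specially reviewed the data related to potential neurotoxicity", and that the review covered nerve conduction studies and found a low incidence of neuropathies and abnormalities. Protocol 6.5 lists "Severe Neurotoxicity considered related to the IMP" among the reasons for stopping study treatment.

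In the extension, Protocol 8.2.1 directs the neurological examination at peripheral nerve dysfunction, including "diminished or absent reflexes (compared with baseline examination), sensory abnormalities (e.g. numbness or tingling) or weakness", and requires sites to enter every abnormal finding in the database. Table 1 schedules this examination at baseline and every 6 months.

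On recording, Protocol 9.1.1 says "Changes in ALS symptoms will not be documented as AEs unless they are extraordinary and/or unexpected".

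On reporting, Protocol 11.3.5 and 11.3.5.1 promise tabulation of physical-examination abnormalities, and 8.2.1 counts neurologic evaluation as part of the physical examination. SAP 5.6.2, on other safety endpoints and examinations, reads "Not applicable / not in the scope of this SAP following early termination of the study". SAP 9.4 puts listings out of scope.

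**The concern.** The primary objective is long-term safety and the primary endpoint is treatment-emergent adverse events. For peripheral neurotoxicity, part of the clinical picture looks like the disease. A motor or reflex sign that the investigator attributes to ALS need not become an adverse event, so it never reaches the causality assessment in Protocol 9.4 or any TEAE table. That would matter less if the examination findings were reported, because a reader could then see how often nerve-related abnormalities arose whatever their attribution. The SAP reports none of them. What is at stake is the ability to interpret the neuropathy-type TEAE count, and in particular to check a low count against the examination that was scheduled to look for the problem.

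**Working it through.** No figure in the documents bears on this point, so the check sets the sections side by side.

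**1. Which signs are shared.** Protocol 2.1 says that lower-motor-neuron degeneration "results in loss of muscle strength, muscular atrophy, hyporeflexia, hypotonicity, fasciculations, flaccidity and or muscle cramps".

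| Sign sought in Protocol 8.2.1 | Among the ALS signs in Protocol 2.1? | Route into the adverse-event data |
|---|---|---|
| Motor symptoms, weakness | Yes (loss of strength) | If judged to be ALS: only when extraordinary or unexpected |
| Diminished or absent reflexes | Yes (hyporeflexia) | Same |
| Sensory abnormalities | Not listed | Ordinary adverse-event recording |

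Neither extraordinary nor unexpected is defined for ALS symptoms. Protocol 9.1.3 defines unexpectedness for adverse reactions against the reference safety information, which is a different question. No rule is given for telling progression from a drug effect.

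**2. What else could detect it.** Table 1 and Protocol 6.2 and 6.3 contain no nerve conduction studies. Detection rests on the 6-monthly examination and on adverse-event monitoring at the 3-monthly visits. For patients who can no longer travel, Protocol section 6 sets the minimum data for staying on study medication as laboratory tests, adverse events and ALSFRS-R. The neurological examination is not in that minimum, so for these patients the adverse-event route carries most of the weight.

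**3. What is reported.** SAP 9.3 lists these outputs under 14.3:

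- 14.3.1.1 to 14.3.1.4: overview of adverse events, TEAEs, serious TEAEs, and TEAEs leading to discontinuation (4 entries).
- 14.3.2.1 and 14.3.2.2: deaths and TEAEs (2 entries).

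That is 4 + 2 = 6 entries. All rest on adverse-event or death records, and none shows an examination finding. SAP section 6 says in general terms that scope is reduced after early termination. It does not say that the examination tabulation in Protocol 11.3.5.1 is lost.

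**4. Whether ALSFRS-R fills the gap.** SAP 5.5.2.2 gives descriptive ALSFRS-R scores and change from the extension baseline. The scale measures function, not its cause, and SAP 3.1.2 notes that all patients receive FAB122 in the extension. These summaries cannot separate toxicity from progression.

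**5. The reference point.** The extension baseline is normally ADORE Visit 6 or 8, and Protocol 2.1 puts ADORE participation at 48 and up to 72 weeks. For patients randomised to FAB122, that baseline follows long exposure. A comparison with it alone shows change during the extension, not change since first exposure.

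**The case against.** The strongest reply is that the exemption is narrow. It covers changes in ALS symptoms, not every sign that might be ALS or drug, and it keeps extraordinary or unexpected changes recordable. The same section defines an adverse event as any unfavourable sign, related or not. Sites are told to look for peripheral nerve dysfunction, to ask about adverse events at each visit, and to have patients with symptoms at home contact the clinic. Exempting expected progression is a sensible way to limit noise in ALS. All of this stands. The gap is confined to motor and reflex worsening that has already been attributed to ALS.

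A reader might go further in four ways that the documents do not support.

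- That the TEAE count for neurotoxicity must be too low, or that a low neuropathy rate would be reported whatever the truth. Sensory events should still be recorded and would appear in the SOC and preferred-term table, and in the discontinuation table if treatment stops. The count can respond to real toxicity.
- That damage present at the extension baseline is treated as normal. Protocol 8.2.1 attaches the baseline comparison to reflexes only, and separately requires all abnormal findings to be documented.
- That 9.1.1 should be rewritten so that every new weakness or reflex change is an adverse event. The study had already terminated early when the SAP was finalised, so new wording could not change what was collected. In a cohort where everyone is treated, it would also fill the primary endpoint with disease progression.
- That 9.1.1 caused the missing output. The omission comes from the general SAP reduction, which also removes laboratory, ECG and vital-sign summaries.

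It is also fair to object that the CRF is not among the documents, so the findings may be held as free text. That affects the cost and detail of a table, not the case for having one.

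**Conclusion.** The point holds as a reporting gap. Motor and reflex worsening judged to be ALS may not be recorded as an adverse event, and the examination findings that could partly compensate appear in none of the six planned safety outputs, although the protocol undertook to tabulate physical-examination abnormalities. Its size in patients or events cannot be given, because the documents contain no rate of neurotoxicity or of misattribution. Nothing in them shows that an under-count has occurred.

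The conclusion assumes that the neurological findings were entered in the database as Protocol 8.2.1 requires, and that the physical-examination tabulation in 11.3.5.1 was meant to include the neurologic part, since no separate neurological analysis is described. Early termination explains a shorter report, but it does not remove the value of showing safety data already collected for a primary safety objective.

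**What to change.** Add to SAP section 14.3 a descriptive table on the SAFe set of neurological-examination abnormalities by visit and ADORE randomised group. Show sensory abnormalities separately from weakness and reflex change, as far as the CRF coding allows, because they are the findings least confounded with ALS. Give results against the extension baseline and, where an ADORE baseline examination is available, against that as well.

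State with the table that weakness and reflex findings cannot separate drug effect from ALS progression without a concurrent control. Note also that the ADORE groups are selected by the time they enter the extension, since Protocol 5.3 keeps patients who stopped the drug in ADORE for safety reasons off extension treatment.

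In SAP section 6, name the examination outputs that are dropped relative to Protocol 11.3.5 and 11.3.5.1.

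The cost is one table, a sentence or two of text, and possibly some coding of free-text findings. No visit, procedure or change to Protocol 9.1.1 is needed.
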